CLINICAL TRIAL PROTOCOL

Light and Ion Treatment to Enhance⁺ Medication Efficacy in Depression

(The LITE+MED Trial)

A Randomized Controlled Trial of Light Treatment and Fluoxetine in Patients with Nonseasonal Major Depressive Disorder

Principal Co-Investigators:

[name], University of British Columbia
[name]
[contact], [contact], [contact]

[name], University of Toronto

[name], University of Toronto

[name], University of BC

[name], University of Manitoba

[name], University of Toronto

[name], University of Toronto

[name], Sunnybrook Health Sciences Centre

[name], MDCM, McGill University

[name], Dalhousie University

[name], University of Calgary

[name], University of Calgary

Revised Version Date: November 18, 2010

CLINICAL TRIAL PROTOCOL

Light and Ion Treatment to Enhance+ Medication Efficacy in Depression.

A Randomized Controlled Trial of Light Treatment and Fluoxetine in Patients with Nonseasonal Major Depressive Disorder.

i. Table of Contents

A. Objectives	2
B. Overall Study Design	2
C. Outcome Measures	3
D. Study Population	5
E. Treatments	7
F. Procedures and Methods	8
G. Concomitant Therapy	9
H. Data Safety Monitoring Committee ...	10
I. Quality Assurance	10
J. Early Termination	11
K. Data Analysis	11
L. Informed Consent and Ethics	11
M. Publications and Communications	12
N. List of Investigators	12
O. References	12
P. Appendix: Summary of Procedures...13	

A. Study Objectives

The **primary objectives** of this study are to test the hypotheses that, in patients with nonseasonal major depressive disorder (MDD) of at least moderate severity: 1) light treatment with a fluorescent light box (10,000 lux white light for 30 minutes daily) is more effective than a placebo control condition, and 2) combined light treatment and antidepressant medication (fluoxetine) is more effective than placebo and both monotherapies.

The **secondary objectives** of this study are to investigate the effects of bright light treatment and fluoxetine on clinical response and remission rates, adverse events, quality of life, work productivity, and health services utilization.

[figure not shown]
B. Overall Study Design (see Figure 1)

This trial has been designed as a multicentre, double-blind, placebo-controlled, randomized, parallel-design study. A total of 216 patients meeting entry criteria will be enrolled at 6 centres over a 3 year period.

Phase I is a one week baseline phase without treatment to quantify baseline pre-treatment measures (see Figure 1). In **Phase II**, subjects will be randomized to 1 of 4 treatment conditions for 8 weeks: 1) active light treatment using a fluorescent light box (10,000 lux white light for 30 minutes daily) plus a placebo pill, 2) placebo inactive negative ion generator (30 minutes daily) with fluoxetine 20 mg/d, 3) placebo inactive negative ion generator (30 minutes daily) plus placebo pill (double placebo), or 4) combined active light treatment using a fluorescent light box (10,000

lux white light for 30 minutes daily) plus fluoxetine 20 mg/d. Randomization will be conducted centrally via a web-based computerized system and stratified by sex and centre.

Figure 1. Protocol Summary (also see Appendix 1 – Summary of Procedures)

The primary measure of efficacy will be change score (baseline to termination) on the Montgomery-Asberg Depression Rating Scale (MADRS). Secondary measures of efficacy will include clinical response (50% or greater improvement in MADRS scores) and remission (final MADRS score of 10 or less), scores on the 24-item Hamilton Depression Rating Scale (Ham-24), the CGI, the Quick Inventory of Depressive Symptoms (QIDS-SR, Rush 2003), the Lam Employment Absence and Productivity Scale, and the Quality of Life, Enjoyment and Satisfaction Questionnaire. All of these outcome measures are widely used in depression research studies, are sensitive to change, and have been well validated (e.g., Lam et al, 2005). Safety and adverse events data will also be systematically recorded and compared across conditions. Utilization of health services data will be captured to estimate cost-effectiveness of each active treatment condition compared to placebo.

C. Outcome Measures (see Appendix 1)

1. Montgomery-Asberg Depression Rating scale (MADRS, Montgomery and Asberg, 1979). This interview-rated 10-item is also used widely for depression studies and is sensitive to change in clinical trials. Reliability is enhanced by using the Structured Interview Guide for the MADRS (SIGMA, Williams et al, 2008). To further increase reliability and maintain integrity of the blind, patients will be rated by telephone raters blind to treatment condition. The telephone rating method is widely used in depression studies, has been validated against face-to-face interviews, and has been used regularly at several centres in this trial. The MADRS is more reliable than the Ham-D in telephone ratings.
2. Hamilton Depression Rating Scale (Ham-D, Hamilton, 1967). The interviewer-rated Ham-D is the most widely used measure of outcome in depression studies. To enhance reliability, a semi-structured interview, the Structured Interview Guide for the Hamilton Depression Rating Scale

- (SIGH, Williams et al, 1988). The SIGH generates scores for several versions of the Ham-D, including the 17-item Ham-D (Ham-17), which is the most widely used outcome measure in depression clinical trials. The SIGH also generates a 7-item atypical symptom addendum, for a 24-item total (Ham-24). This atypical addendum was developed because the original Ham-17 does not rate depressive symptoms such as hypersomnia, increased appetite, and weight gain.
3. Quick Inventory of Depressive Symptoms, Self-Rated version (QIDS-SR, Rush et al, 2003). This self-rated depression inventory is also widely used and validated in depression studies. It will provide a basis for comparison to the results from the large U.S. STAR*D trial.
 4. Clinical Global Impression scale, Severity and Improvement (CGI, Guy 1976). The CGI adds an overall clinical impression to the continuous outcome measures, and is useful as a global measure of change.
 5. The Adult ADHD Self-Report Scale (ASRS-v1.1) is a self-rated scale that assesses the severity of 18 symptoms associated with Attention Deficit/Hyperactive Disorder (ADHD) (Kessler et al., 2005). This scale is used as a screening tool for adults who exhibit symptoms of ADHD, and provides information to the clinician regarding the need for more in-depth clinical interview (Schweitzer et al., 2001; Barkley, 1998). The questions in the ASRS v1.1 are consistent with the DSM-IV criteria and manifestations of ADHD symptoms, and has high validity and reliability (Adler et al., 2006; American Psychiatric Association, 2000).
 6. Adverse Events Scale (CANMAT, 1999). Developed by the Canadian Network for Mood and Anxiety Treatment for use in the Emergency Drug Release program, this self-rated scale assesses both frequency and severity of 32 adverse events (including a category for “other”). This scale provides a more comprehensive and systematic evaluation of adverse events than is usually conducted in antidepressant clinical trials, and was used in the CIHR-funded CAN-SAD light treatment versus fluoxetine study (Lam et al, 2006).
 7. Lam Employment Absence and Productivity Scale (LEAPS, Lam, 2007). This 10-item self-report scale assesses absenteeism and presenteeism (work productivity) and has recently been validated in depressed patients.
 8. Quality of Life, Enjoyment and Satisfaction Questionnaire (Q-LES-Q, Endicott et al, 1993). The Q-LES-Q is a 16-item self-report questionnaire developed and validated for use in depressed outpatients. There are also single items that rate “overall life satisfaction and contentment” and “satisfaction with medications (if any are taken).” The Q-LES-Q has good test-retest reliability and is sensitive to change in clinical status.
 9. Pittsburgh Sleep Quality Index (PSQI) (Buysse et al., 1989). The PSQI is a subjective instrument used to assess the quality and pattern of sleep in adults. Patients score themselves on seven areas of sleep, including subjective sleep quality, sleep latency, sleep duration, habitual sleep efficiency, sleep disturbances, use of sleeping medication, and daytime dysfunction. The PSQI has good reliability and validity for use in adults across all health care settings (Buysse et al.).
 10. Fatigue Severity Scale (FSS, Krupp et al., 1989). This 9-item scale is designed to differentiate fatigue from clinical depression, as they exhibit similar symptoms. This scale is also a practical

measure due to its brevity and ease of administration/scoring (Friedberg & Jason, 1998; Krupp et al., 1989).

11. Health Economic Assessment (HEA, Fantino et al, 2007), to assess health care utilization and costs associated with the various treatment conditions.
12. Seasonal Pattern Assessment Questionnaire (SPAQ, Rosenthal et al, 1987). The SPAQ is widely used as a screening tool for SAD and to assess seasonality as a dimensional construct.
13. Morningness-Eveningness Questionnaire (MEQ, Horne and Ostberg, 1976). This questionnaire has been used in many studies to establish a chronotype – the propensity for optimal mood and alertness to occur in the morning or evening. Scores on the MEQ have been significantly correlated with physiological measures of circadian phase.
14. Relationship Styles Questionnaire (RSQ, Griffin & Bartholomew, 1994). This questionnaire assesses general orientations and attachment styles in close relationships. This instrument has good internal consistency and test-retest reliability, and results correlate well with attachment data provided by other informants pertaining to the respondent (Creasey et al., 2004; Griffin et al., 1994). The RSQ is frequently used as a screening tool for attachment styles across a variety of clinical settings, and has good convergent validity with other attachment scales (Creasey et al., 2004; Eames & Roth, 2000).

D. Study Population

Entry Criteria

Clinical trials for depression have always used clinic samples of patients rather than epidemiologically sampled patients, because of convenience. Results are then generalizable to those patients who are willing to seek help (epidemiological studies show that 50% of people who suffer from major depression do not seek help). An advertising strategy will be used to recruit patients for this study. We and others have been using this strategy for clinical trials that require rapid recruitment. Patients recruited through advertisement are similar to those recruited from the clinic, but are not usually as resistant to treatment.

Participation will be voluntary. The nature of the study will be fully explained to the patient. The patient must have an educational level and degree of understanding such that he/she can communicate with the investigator and research staff intelligently. An informed consent document (ICD) will be signed by the patient and retained by the investigator. A signed copy will be given to both the patient and to the Study Coordinator. Patients should be reliable and must agree to keep appointments for clinic visits and all tests and examinations required by the protocol. All patients will be screened using the Mini International Neuropsychiatric Interview (MINI, Sheehan et al, 1998) to confirm the diagnosis and to rule out other primary illnesses (such as bipolar disorder, other depression/anxiety disorders, substance abuse, etc.). All patients will also be evaluated for risk of suicidality, using the Columbia Classification Algorithm of Suicide Assessment (C-CASA, Posner et al, 2007).

Inclusion Criteria

1. Male and female outpatients aged 19-60 years.
2. Patients will meet criteria for major depressive episodes as determined by a structured interview (Mini Neuropsychiatric Interview, MINI, Sheehan et al, 1998).

3. A score of 20 or greater on the clinician-rated Ham-17, indicating at least moderately severe depression, comparable to previous depression treatment studies.
4. Competency to give informed consent.

Exclusion Criteria

1. Pregnant women, lactating women and sexually active women of childbearing potential who are not using medically accepted means of contraception.
2. Serious suicidal risks as judged by the clinician, the MINI, the Ham-17, and the C-CASA.
3. The following DSM-IV diagnoses (to ensure a homogenous diagnostic group):
 - Major depressive disorder, recurrent, with a seasonal pattern
 - Organic mental disorders
 - Substance abuse/dependence, including alcohol, active within the last year
 - Schizophrenia, Paranoid or Delusional Disorders, or any other psychotic features
 - Obsessive-Compulsive Disorder, Post-Traumatic Stress Disorder
 - Panic disorder, Generalized Anxiety Disorder, if a primary diagnosis
 - Bipolar Disorder
 - Bulimia Nervosa; Anorexia Nervosa
4. Serious illness including cardiac, hepatic, renal, respiratory, endocrinologic, neurologic and hematologic disease that is not stabilized, or a past history of convulsions.
5. Any retinal disease or systemic illness with active retinal involvement (e.g. diabetes) that precludes the use of bright light.
6. Patients who have a history of severe allergies and multiple drug adverse reactions.
7. Regular or current use of other psychotropic drugs including lithium and tryptophan.
8. Patients treated with beta blocking drugs.
9. Hypertensive patients being treated with guanethidine, reserpine, clonidine or methyldopa (because of possible mood-altering effects of those drugs).
10. Use of monoamine oxidase inhibitors within 14 days of Visit 1 (to ensure no drug interactions between fluoxetine and MAOIs), or use of heterocyclic antidepressant within 7 days of Visit 1 (to ensure adequate washout period of two weeks between stopping previous drug and start of treatment at Visit 2).
11. Previous use of fluoxetine or light therapy.
12. Treatment resistance in the current episode, as defined by failure (lack of clinically significant response) of two or more antidepressants given at therapeutic doses for at least 6 weeks.
13. Patients who started formal psychotherapy (e.g. cognitive-behavioural or interpersonal psychotherapy) within 3 months of Visit 1, or who plan to initiate such psychotherapy during this study.
14. Patients involved in any other form of treatment for depression.

Sample Size

Based on a power analysis using a minimal clinically important difference (MCID) and data derived from the largest and highest quality study of light and medication treatment for MDD (Martiny et al, 2005), we propose a sample size of 216 patients overall, or at least 54 randomized to each of the 4 groups with allowance for a 20% dropout rate (the average in our previous studies), recruited over 3 years. With regard to the primary hypothesis, this sample size will allow us to detect a difference of 3.5 points on the MADRS (widely regarded as a MCID in depression

treatment studies) between conditions with 80% power at two-sided testing at a Bonferroni-corrected $\alpha=0.017$ (3 planned comparisons: fluoxetine vs. placebo, light vs. placebo, light+fluoxetine vs. placebo).

For the secondary hypotheses, a sample size of 216 patients will allow us to detect a risk difference in response or remission rates of 15% between conditions. It also allows us to detect a minimal difference between means of at least 5 points on scale scores such as quality of life measures, based on an anticipated pooled standard deviation of 8 points (based on previous studies, e.g., Michalak et al, 2005), at 80% power and an alpha of 0.05 on two-sided testing. Again, these differences are considered clinically meaningful and are similar to the effect sizes seen in meta-analyses of antidepressant drugs vs. placebo.

E. Treatments

Treatment Device Method

The active treatment consists of a fluorescent (4000 Kelvin broad spectrum) light box that emits 10,000 lux ($2600 \mu\text{w}/\text{cm}^2$) white light measured by digital photometer at the level of the cornea when subjects are positioned at 18 inches from the screen. The light box will be fitted with a screen that filters out wavelengths below 400 nm (ultraviolet wavelengths).

Subjects will be given standardized instructions on how to use the light box (supplied by Uplift Technologies, Canada). In summary, subjects will be instructed about properly positioning themselves and the light box to maintain the correct distance to the light source. A measuring cord attached to the light box will be used to ensure that the distance is properly maintained. They will be instructed to stay awake with their eyes open during light exposure, but they will not be required to look directly at the light source, i.e., they can read or eat during the light treatment. The instructions will be repeated at each clinic visit. Subjects will take home the light box and sit under the light box for 30 minutes, within 15 minutes of arising from habitual wake time.

The placebo control treatment consists of a negative ion generator (SphereOne Inc.) modified to emit an audible hum, but which is deactivated so no negative ions are emitted. This credible placebo condition has been used in previous studies by our group and others (Desan et al, 2007; Eastman et al, 1998; Goel et al, 2005).

The same instructions as used for the light box will be used for the ion generator. Patients will be instructed to use the ion generator for 30 minutes, within 15 minutes of arising from habitual wake time.

To improve and monitor adherence to the protocol, each treatment device will be fitted with a computer chip that records the time when the device is turned on. This will provide a post hoc assessment of treatment adherence.

Antidepressant Medication Method

Study drugs will be administered on a once-a-day (morning) treatment regimen. At each visit patients will be given bottles from their randomly assigned patient kits. Each capsule will contain either fluoxetine (20 mg), or placebo. A capsule count will be taken at each visit throughout the study and recorded on the web-CRF (Case Report Form).

F. Procedures and Methods (also see Summary of Procedures, Appendix 1)

The study begins with a screening visit to establish eligibility for the study and to obtain informed consent. A script will be used to explain the study objectives to subjects. They will be told that the study will involve taking active or inactive treatments, including a placebo pill, and that we are studying different light and ion treatments that may or may not be effective. A similar script and procedure has been approved by the IRB in previous UBC light treatment studies.

Once patients have agreed to participate in the study by signing the ICD, the following will then be completed and recorded:

1. Full medical and psychiatric history, including the MINI.
2. Structured Interview Guide for the Hamilton Depression Rating Scale (HAMD), which generates the Ham-17 with established reliability.
3. CGI-Severity
4. Seasonal Pattern Assessment Questionnaire (SPAQ).
5. Adult ADHD Self-Report Scale (ASRS)
6. Relationship Styles Questionnaire (RSQ)

Study Phase I

Study Phase I, lasting one week, is an initial observation period to establish baseline pre-treatment routines. It commences at Visit 1 (screening) and finishes at Visit 2 (randomization). Subjects will keep track of sleep times, treatment device times, and times spent outdoors in a daily log that will be collected at each weekly visit. Visits for other health-related services (family physician, emergency room, etc) will also be tracked using the Health Economic Assessment.

Study Phase II

Study Phase II is an 8-week, “double-blind” treatment period that commences at Visit 2 (randomization visit). Subsequent evaluation will be scheduled at one-week intervals for the first 2 visits, then two-week intervals for the next 3 visits, concluding at Visit 7, or upon termination. During this treatment phase, patients will take one tablet of study medication (fluoxetine 20 mg, or placebo) daily and will use the treatment device (light box or ion generator) for 30 minutes daily.

At Visit 2, patients will be discontinued from the study if they show significant spontaneous response. Spontaneous response is defined as greater than 25% reduction of Ham-17 between Visit 1 and Visit 2, or if the Ham-17 at Visit 2 is 19 or less.

At Visit 2, subjects will be instructed on the use of the assigned treatment device and medication, and will then complete an Expectation of Response questionnaire modeled on a questionnaire by Borkovec and Nau (1972). Subjects will take home the treatment device to use for the duration of the study. Adherence to the protocol will be reinforced and monitored at each study visit. A daily log will be completed by subjects to record their use of the treatment device, and they will telephone the Centre and leave a time-stamped voice-mail message each day when using the device. These logs will be inspected at each visit throughout the study and recorded on the web-CRF.

In summary, the following clinical efficacy parameters will be recorded at Visit 2.

1. Expectation of Response Questionnaire (Visit 2 only)
2. Ham-17

The following clinical efficacy and safety parameters will be repeated at Visits 2 through 7.

1. Combined MADRS/Ham-24 (by telephone with a rater blind to treatment condition using the SIGMA/SIGH-SAD)
2. CGI (Severity and Improvement)

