A secondary confirmatory analysis will also be conducted using a mixed-effects model with repeated measures (MMRM), under the missing at random framework (Gueorguieva and Krystal, 2004). The baseline MADRS score will be used as a covariate under this model. This model will include treatment condition and visit factors as class fixed effects and subject as random effect as well as two interaction terms between treatment condition by visit and covariate by visit, and subject as random. The treatment condition factor will have 4 levels (two monotherapies, one placebo condition, and one combination condition) and the visit factor will have 4 levels (each of the 4 treatment visits). This model using all available post-baseline evaluation in Phase II will provide the baseline adjusted least-squares means (LS-means) estimates at Week 8 by treatment condition, as well as the differences of these estimates versus placebo conditions, with their corresponding standard errors, degrees of freedom, t-test statistics and associated 95% confidence intervals. The t-test statistic at Week 8 will be used to determine the statistical significance of the primary efficacy comparisons of active versus placebo conditions.

L. Informed Consent and Ethical Considerations

The investigator will prepare a written Informed Consent Document (ICD). The subject will read the ICD and the investigator will answer any questions he/she may have. The subject must indicate willingness to participate in the study by signing the ICD. The document must also be signed by a witness and an investigator. A copy of the signed ICD will be submitted to the Study Coordinator.

This study will be conducted according to guidelines established by Good Clinical Practice (Food and Drug Administration, www.fda.gov/oc/gcp/regulations.html). The Institutional Review Boards (IRBs, or research ethics committees) of each participating site must approve the protocol and ICD. Each investigator will provide the Study Coordinator with evidence that their IRB has approved the study before subjects are entered at that site.

M. Publications and Communications

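### Primary objective 2 claims superiority over both monotherapies, but the protocol lists, allocates alpha to and powers only the comparisons with placebo

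*Protocol*

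**What the plan says.** Section A (Study Objectives) gives two primary hypotheses. The first is that light "is more effective than a placebo control condition". The second is that "combined light treatment and antidepressant medication (fluoxetine) is more effective than placebo and both monotherapies".

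The Sample Size part of section D sets the error rate and the power. The trial is sized to "detect a difference of 3.5 points on the MADRS" with "80% power at two-sided testing at a Bonferroni-corrected $\alpha=0.017", and the divisor is explained by "3 planned comparisons: fluoxetine vs. placebo, light vs. placebo, light+fluoxetine vs. placebo". The allocation is "at least 54 randomized to each of the 4 groups with allowance for a 20% dropout rate", 216 in total.

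Section K (Data Analysis) says that the primary ANOVA on MADRS change will use pairwise contrasts fixed in advance, but it does not name them. The supporting mixed model in the same section yields adjusted means for each condition "as well as the differences of these estimates versus placebo conditions", and its Week 8 test is tied to active-versus-placebo comparisons.

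**The concern.** Objective 2 joins three statements about the combination: better than placebo, better than light, better than fluoxetine. Only the first is on the list of planned comparisons. Fluoxetine versus placebo, which belongs to neither primary hypothesis, takes one of the three alpha shares.

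The two unlisted contrasts are the ones that carry the question of whether combining treatments is worthwhile. A difference between combination and placebo can come entirely from one component, so it does not show that the other adds anything. A reader of the final report could not tell from the protocol whether a monotherapy comparison was confirmatory, at what level it was tested, or what chance it had of succeeding. The 80% in section D could also be taken to apply to objective 2 as a whole.

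**Working it through.** **1. Match hypotheses to planned comparisons.**

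| Contrast | Needed by section A | Listed in section D |
|---|---|---|
| Light vs placebo | yes (objective 1) | yes |
| Combination vs placebo | yes (objective 2) | yes |
| Combination vs light | yes (objective 2) | no |
| Combination vs fluoxetine | yes (objective 2) | no |
| Fluoxetine vs placebo | no | yes |

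**2. Reproduce the stated alpha.** 0.05/3 = 0.0167, which rounds to 0.017. This agrees with three comparisons. The four that the objectives need would give 0.05/4 = 0.0125, so the stated alpha was built on the placebo-only list.

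**3. Recover the implied standard error.** The protocol gives no SD for MADRS change, so the sample size cannot be reproduced directly. For a two-sided normal test, 80% power requires difference / SE = z(1 − 0.017/2) + z(0.80) = 2.387 + 0.842 = 3.228. With a difference of 3.5, the SE of a pairwise difference is 3.5/3.228 = 1.084. Since SE = SD × √(2/n), the implied SD is 5.03 with 43 evaluable per arm (54 less 20% dropout), or 5.63 if all 54 are analysed. The power results below depend only on the SE, so they are the same for both.

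**4. What combination vs placebo shows by itself.** Suppose light and fluoxetine each gain 3.5 points over placebo and the combination also gains 3.5, so that it adds nothing. The combination-placebo contrast then has a true difference of 3.5 and is significant with probability 0.80. The same 0.80 applies if light is inert and fluoxetine alone supplies the 3.5 points.

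**5. Power for the whole of objective 2.** Four independent arm means were simulated, each with SE 1.084/√2. All three combination contrasts had to be significant in favour of the combination at two-sided 0.017.

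| True gain over placebo (light, fluoxetine, combination) | Combination beats all three |
|---|---|
| 3.5, 3.5, 7.0 (full additivity) | 0.69 |
| 3.5, 3.5, 5.5 (2 points over each) | 0.15 |
| 3.5, 3.5, 3.5 (nothing added) | 0.001 |

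As a check on the second row, one contrast with a true difference of 2 points has power Φ(2/1.084 − 2.387) = 0.29. Requiring two such contrasts that share the combination arm must give less.

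**6. Familywise error if objective 2 requires all three contrasts.** Under the global null, the simulated familywise error of the three listed contrasts at 0.017 is 0.045. Adding the objective 2 claim leaves it at 0.045, because that claim can be made only when combination vs placebo has already been rejected. If combination vs placebo is truly non-null, its alpha share cannot produce a false rejection. A false objective 2 claim then has probability at most 0.017, because at least one of its required legs is null. The Bonferroni bound of 3 × 0.017 = 0.051 (0.05 before rounding) therefore still holds.

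**The case against.** The strongest reply has four parts.

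- **Objective 2 is partly covered.** Combination versus placebo is planned, powered and given alpha. All four arms are randomized and measured, the contrasts named generically in section K are not restricted to placebo, and the mixed model gives a mean for every arm. This stands. A reader might infer that objective 2 is never tested or that the trial cannot answer it. The protocol does not support that: the gap is confined to the two monotherapy legs of the confirmatory plan.
- **An unseen SAP may list the contrasts.** It may, but the protocol is not silent here. It counts three comparisons, names them and derives alpha from the count. That list conflicts with section A whatever the SAP says.
- **No passage says that combination versus placebo will be taken as proof of objective 2.** Correct. Nor is that contrast significant whenever a component works; the 80% applies to a 3.5-point effect. The figure shows what the listed contrast can and cannot distinguish, not what the investigators intend to claim.
- **Adding the contrasts need not inflate error.** A reader might expect it to, since five separate claims at 0.017 give a familywise error of 0.069 under the global null. That figure does not describe objective 2, which is a conjunction. With all three legs required, the error stays at 0.045.

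The mixed model is also only a supporting analysis, so its placebo-only scope is corroboration and not the core of the point.

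**Conclusion.** The point holds in this limited form. Sections A and D contradict each other on what the primary comparisons are, and section K repeats the placebo-only scope. The superiority-over-monotherapy part of objective 2 has no listed contrast, alpha or power, and the stated 80% does not cover objective 2. Under the plan's own implied precision, joint power is about 0.69 with full additivity and falls quickly with a smaller added benefit.

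These power figures assume the back-solved standard error, a normal approximation and equal arm sizes. Full additivity and the 2-point gain are illustrations; the protocol states no expected difference between the combination and a monotherapy. The contradiction itself depends on none of these assumptions. Listing fluoxetine versus placebo as a planned contrast is not an error in itself.

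**What to change.** In the Sample Size part of section D, and in both the ANOVA and mixed-model parts of section K, add combination versus light and combination versus fluoxetine as planned primary contrasts. State that objective 2 is met only if all three combination contrasts favour the combination and are significant at the existing 0.017. By step 6 no further alpha adjustment is needed. State the power for objective 2 separately from the 80% per placebo contrast, with the SD and the assumed gain over each monotherapy.

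An acceptable alternative, not required, is to apply Holm to the two hypotheses (light versus placebo, and the largest of the three combination p-values) with fluoxetine versus placebo outside the family.

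The cost is wording. Valid testing needs no extra patients or data. The price is that the stated power for objective 2 becomes less favourable.
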